## 8.0 Sharing of Results with Subjects\*

- 8.1 Results will not be shared with subjects unless any incidental findings arise and only the PI will notify the subject directly of the finding and consult with them and discuss if they believe they should seek further medical attention if appropriate. Results will not be shared with any other medical providers without the subject's knowledge or permission within the scope of this study. The investigators do not anticipate this situation to occur frequently due to the nature of this protocol.

## 9.0 Study Timelines\*

- 9.1 This is a 6-week randomized controlled trial that consists of all subjects to complete 2 in person visits of 1.5-2 hours in the READY Laboratory (first and last exercise sessions). There are planned follow up visits with questionnaires through REDCap at 12-, 18-, and 24-months following completion of the intervention. We expect to enroll and collect data for all subjects within a 4-month time frame from the start of enrollment. We estimate this study to be completed and

primary analyses to be completed within 8 months of the start of enrollment.

## **10.0 Inclusion and Exclusion Criteria\***

10.1 Individuals will be screened for inclusion and exclusion criteria by self-reporting while reading the consent form and prior to giving consent.

10.2 *Inclusion Criteria:* ages 18-45, biological sex of Male or Female, self-reported low back pain within the previous 6 months or greater than 3 episodes within the past 3 years

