## Study Summary

Study Title	The Effects of a Gamified Rehabilitation Protocol Compared to an At-Home Exercise Packet in Individuals with Low Back Pain
Study Design	Randomized Controlled Trial
Primary Objective	To measure the change in pain and disability before, during and after a competitive home exercise program compared to a take home packet exercise program.
Secondary Objective(s)	
To quantify adherence and compliance of individuals completing a competitive, gamified home exercise program compared to a traditional autonomous exercise program.
 
To measure the change of Ultrasound thickness and onset of muscle activation of the lateral abdominal wall in individuals with non-specific low back pain during static and exercise positioning following a 6-week home exercise program

Research Intervention(s)/Investigational Agent(s)	None
IND/IDE #	N/A
Study Population	
Individuals aged 18-45 with non-specific low back pain
 
Inclusion Criteria: ages 18-45, biological sex of Male or Female, self-reported low back pain within the previous 6 months or greater than 3 episodes within the past 3 years
 
Exclusion Criteria: Currently seeing and or receiving care from an athletic trainer, physical therapist, or other rehabilitation specialist in the previous 6 months, low back pain conditions such as lumbar spondylosis, herniated disc, spondylolisthesis, previous spine surgery, currently pregnant, experiencing neurological symptoms or other muscular abnormalities.
 
Unable to assume the exercise starting position.
 
Current use of lidocaine patches or prescription pain medicine.

Sample Size	40
Study Duration for individual participants	6-week intervention + 12, 18, 24-month follow-ups
Study Specific Abbreviations/ Definitions	NSLBP: non-specific low back pain; ODI: Oswestry Disability Index; NPRS; Numeric Pain Rating Scale; SUS: System Usability Scale; EARS: Exercise Adherence Rating Scale; CES: Credibility and Expectancy; PCS: pain catastrophizing scale; PBP: Prone Bridge Plank; GROC; Global Rating of Change Scale; TESP: Torso Elevated Side Plank; FESP: Foot Elevated Side Plank; TrA: Transverse abdominis; IO: Internal oblique; EO: External oblique

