### *Exclusion Criteria:*

- Currently seeing and or receiving care from an athletic trainer, physical therapist, or other rehabilitation specialist in the previous 6 months,
- low back pain conditions such as lumbar spondylosis, herniated disc, spondylolisthesis, previous spine surgery, currently pregnant, experiencing neurological symptoms or other muscular abnormalities.
- Unable to assume the exercise starting position.
- Current use of lidocaine patches or prescription pain medicine.

10.3 Adults unable to consent, pregnant women, prisoners, and individuals who are not yet adults, including, infants, children, and teenagers will not be allowed to participate in this study.

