## **12.0 Local Number of Subjects**

12.1 Based on previous research regarding home exercise and disability with low back pain we determine that 40 participants (20 in each group) will be necessary, alpha set *a priori* to .05. 40 participants include a 15% attrition rate.

12.2 A total of 34 individuals (17 per group) will be adequate with 80% power at an alpha level of .05. We include a 15% attrition rate which results in a total sample size of 40 individuals, 20 in each group

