## **13.0 Recruitment Methods**

13.1 Potential subjects will be recruited from the local community and university area through flyer advertisements,

emails, social media (twitter, Instagram and facebook), digital advertisement on the College of Health Professions and Sciences Research Participant Website as well as word of mouth. The same advertisement will be used for flyers, social media, and digital. Individuals interested in the study will use the email listed on the advertisement flyer. Upon receiving an email for a potential participant, the initial email will be sent to schedule an appointment for the first visit for screening and consent (initial email doc). Reminders about collection will be sent on the day before and if applicable (e.g., afternoon collection) on the same morning. The reminder emails will provide an opportunity for participants to confirm or reschedule (ReminderEmailRCTLBP).

- 13.2 Subjects will be from the local community and that may consist greatly of the university community.
- 13.3 Emails (containing the advertisement flyer) and social media advertisements (same text for both) will be posted to university groups throughout the Institute of Exercise Physiology and Rehabilitation Science (which is where the PI's laboratory is located) as well as targeted toward active groups on campus, i.e. Campus Recreation. All content is the same for the flyer that will be used for email and social media recruitment.
- 13.4 Printed advertisements, email, and social media (twitter, Instagram and facebook) advertisement will be utilized and are included in the IRB submission. All advertisements will be that of the flyer uploaded under "Recruitment materials"
- 13.5 Participants will be paid up to \$75 in gift cards for their time and effort. \$20 will be given after week 3, then \$25 will be given after week 6 and then \$10 for each of the long term follow up times at 12, 18 and 24 months. Due to the lengthy protocol, the completion of 3 weeks, 6 weeks and long term follow up times will be used as times the participants get paid in the event a subject withdraws.

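### Entry on low back pain history alone admits people with no current pain or disability, so a floor effect on the primary outcomes is possible and would lower power below the stated 80%

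*Combined protocol and SAP*

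**What the plan says.** The primary objective in the Study Summary is "To measure the change in pain and disability before, during and after a competitive home exercise program", compared with a take-home packet. Section 2.0 makes the hypothesis a between-group one: lower pain and disability in the gamified arm.

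The only symptom requirement, in Section 10.2 and the Study Summary, is "self-reported low back pain within the previous 6 months or greater than 3 episodes within the past 3 years". The two limbs are alternatives. The second admits someone with no pain in the last 6 months; the first admits someone whose single episode resolved months ago.

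NPRS and ODI are completed at the first visit (Section 6.0, Consent and Screening), but no cut-off on either is tied to eligibility. Section 10.1 bases screening on self-report before consent.

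The exclusions include "Current use of lidocaine patches or prescription pain medicine" and rehabilitation care in the previous 6 months. Part of the recruitment in Section 13.3 is "targeted toward active groups on campus, i.e. Campus Recreation".

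On size, Section 12.2 states: "A total of 34 individuals (17 per group) will be adequate with 80% power at an alpha level of .05". Its basis in Section 12.1 is "Based on previous research regarding home exercise and disability with low back pain", with no effect size, SD, test, sidedness or expected baseline score. Section 17.1 analyses the questionnaires by mean differences, confidence intervals and effect sizes, and mentions neither baseline adjustment nor stratification.

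**The concern.** A participant who scores 0 on a scale at baseline cannot go down on it. If such people are enrolled, both arms contain members in whom the hypothesised improvement cannot appear. The average between-group difference shrinks, and the change scores become a mixture of people who can improve and people who cannot. With 17 evaluable per group there is little slack to absorb this. A null result would then be hard to read: the leaderboard may not work, or there may have been too little to improve. This cannot be repaired after enrolment.

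The exclusions for prescription analgesia and recent care, and the approach to active campus groups, make low baseline scores more likely. They do not show how common such scores will be.

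**Working it through.** **Inputs from the documents.** Alpha .05, power 80%, 17 evaluable per group, 15% attrition, 1:1 allocation (Sections 12.1 and 12.2).

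**Inputs assumed because the documents do not give them.** A two-sided two-sample t-test on change; a share f of participants who are pain-free at baseline; and a control-arm mean improvement m among symptomatic participants of 0 to 1 SD.

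**Step 1: the plan's own figures.** 34 / (1 − 0.15) = 40.0 and 17 / 0.85 = 20, so the attrition step reproduces. The 34 cannot be reproduced, because no effect size, SD or test is stated.

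**Step 2: back-solve the effect.** The standardised difference that 17 per group detects with 80% power at two-sided .05 is d = 0.99 (0.87 if one-sided). The two-sided value is used below.

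**Step 3: simple dilution, SD unchanged.** The detectable difference becomes d × (1 − f).

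| f | diluted difference | power, 17 per group | evaluable n per group for 80% |
|---|---|---|---|
| 0% | 0.99 | 80% | 17 (plan) |
| 10% | 0.89 | 71% | 21 |
| 20% | 0.79 | 61% | 26 |
| 30% | 0.69 | 50% | 34 |

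**Step 4: let the mixture change the variance too.** Symptomatic participants have mean change m (control) or m + 0.99 (leaderboard) with SD 1. Pain-free participants have mean change 0 in both arms, with SD 0 or 0.2. I used 40,000 simulated trials per setting.

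| f | power, m = 0 | power, m = 1 |
|---|---|---|
| 10% | 74% | 66% |
| 20% | 67% | 53% |
| 30% | 59% | 42% |

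The choice of SD 0 or 0.2 for pain-free participants moves these by about 1 point.

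Hand check at f = 20%, m = 1, pain-free SD 0.2, with arm variance (1 − f) × 1 + f × 0.04 + f(1 − f) × (symptomatic mean)²:

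- Control: 0.8 + 0.008 + 0.16 × 1² = 0.968.
- Leaderboard: 0.8 + 0.008 + 0.16 × 1.991² = 1.442.
- Pooled SD: √((0.968 + 1.442) / 2) = 1.098.
- Standardised difference: 0.793 / 1.098 = 0.72, which gives 53% power with 17 per group, as simulated.

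**Step 5: power in the symptomatic participants alone, if entry stays open.** Their number per group is 17 × (1 − f), and the effect in them is 0.99 SD.

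- f = 20%: 13.6 per group, about 70%.
- f = 30%: 11.9 per group, about 64%.
- f = 40%: 10.2 per group, about 56%.

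Stratification therefore helps interpretation but does not restore 80%.

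**The case against.** Several objections are fair, and they limit the point.

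- **The share at the floor is unknown.** The documents give no expected baseline distribution. The NPRS wording is in a separate form; whether it asks about pain now or over a period affects how many score 0. This stands, and it makes the loss conditional.
- **The benchmark is not the trial's own.** The 0.99 SD is back-solved and then assigned to symptomatic participants. If the unnamed earlier research enrolled similarly mild people, its effect may already include some dilution, and the figures above would count it twice. This stands.
- **Pain-free participants are not worthless.** A reader might infer that they contribute nothing to the primary objective. The documents do not support that. The comparison is between arms; someone at 0 can worsen, and arms can differ in recurrence. Section 3.0 cites 66% recurrence within the year among people who seek treatment, and questionnaires continue to 24 months. These participants also inform adherence and ultrasound outcomes. The zero mean change in Step 4 is an assumption.
- **The exclusions and recruitment have other explanations.** Excluding current care and analgesics also limits co-intervention, and campus recreation is one channel among several in Section 13.0. They are suggestive only.

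None of this closes the gap in Section 10.2: no minimum current score appears anywhere, and the planned analysis does not allow for its absence.

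**Conclusion.** The concern holds in conditional form. The criteria admit people with no current pain or disability to a trial of change in pain and disability, so a floor effect is possible and would take power below the stated 80%. Power is about 66-74%, 53-67% and 42-59% at pain-free shares of 10%, 20% and 30%. These figures rest on a two-sided t-test, a back-solved 0.99 SD effect in symptomatic participants, no average change in pain-free ones, and control-arm improvement of 0 to 1 SD.

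A reader might infer that the floor effect removes the trial's power, or that the 80% is shown to be false. Neither follows: the pain-free share is not given, and the 80% cannot be verified in either direction without its effect size and source.

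**What to change.** 1. Add to Section 10.2 a minimum current score on the NPRS and/or ODI, with the level chosen and justified by the sponsor. Both are already collected at the screening visit. State in Sections 6.1 and 10.1 that the score is checked before the allocation envelope is opened. Cost: one eligibility line; some volunteers are screened out and recruitment is slightly slower, though Section 25.1 expects it to be easy.
2. In either case, replace the unadjusted mean differences in Section 17.1 with between-group differences adjusted for the baseline score of each outcome. No new data are needed. This improves precision but does not create room to improve.
3. If entry stays open, stratify allocation by baseline symptom status defined on both NPRS and ODI, and report the symptomatic-stratum estimate alongside the overall one. State that power in that stratum is below 80% (about 70% with 20% pain-free) rather than claim the stated 80%. Cost: a second set of envelopes; nobody is excluded.

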### *Exclusion Criteria:*

- Currently seeing and or receiving care from an athletic trainer, physical therapist, or other rehabilitation specialist in the previous 6 months,
- low back pain conditions such as lumbar spondylosis, herniated disc, spondylolisthesis, previous spine surgery, currently pregnant, experiencing neurological symptoms or other muscular abnormalities.
- Unable to assume the exercise starting position.
- Current use of lidocaine patches or prescription pain medicine.

10.3 Adults unable to consent, pregnant women, prisoners, and individuals who are not yet adults, including, infants, children, and teenagers will not be allowed to participate in this study.

## **11.0 Vulnerable Populations\***

N/A

## **12.0 Local Number of Subjects**

12.1 Based on previous research regarding home exercise and disability with low back pain we determine that 40 participants (20 in each group) will be necessary, alpha set *a priori* to .05. 40 participants include a 15% attrition rate.

12.2 A total of 34 individuals (17 per group) will be adequate with 80% power at an alpha level of .05. We include a 15% attrition rate which results in a total sample size of 40 individuals, 20 in each group

## **13.0 Recruitment Methods**

13.1 Potential subjects will be recruited from the local community and university area through flyer advertisements,

emails, social media (twitter, Instagram and facebook), digital advertisement on the College of Health Professions and Sciences Research Participant Website as well as word of mouth. The same advertisement will be used for flyers, social media, and digital. Individuals interested in the study will use the email listed on the advertisement flyer. Upon receiving an email for a potential participant, the initial email will be sent to schedule an appointment for the first visit for screening and consent (initial email doc). Reminders about collection will be sent on the day before and if applicable (e.g., afternoon collection) on the same morning. The reminder emails will provide an opportunity for participants to confirm or reschedule (ReminderEmailRCTLBP).

- 13.2 Subjects will be from the local community and that may consist greatly of the university community.
- 13.3 Emails (containing the advertisement flyer) and social media advertisements (same text for both) will be posted to university groups throughout the Institute of Exercise Physiology and Rehabilitation Science (which is where the PI's laboratory is located) as well as targeted toward active groups on campus, i.e. Campus Recreation. All content is the same for the flyer that will be used for email and social media recruitment.
- 13.4 Printed advertisements, email, and social media (twitter, Instagram and facebook) advertisement will be utilized and are included in the IRB submission. All advertisements will be that of the flyer uploaded under "Recruitment materials"
- 13.5 Participants will be paid up to \$75 in gift cards for their time and effort. \$20 will be given after week 3, then \$25 will be given after week 6 and then \$10 for each of the long term follow up times at 12, 18 and 24 months. Due to the lengthy protocol, the completion of 3 weeks, 6 weeks and long term follow up times will be used as times the participants get paid in the event a subject withdraws.

## **14.0 Withdrawal of Subjects\***

- 14.1 If subjects no longer meet eligibility requirements or injure themselves, they will be withdrawn from the study by the principal investigator.
- 14.2 N/A
- 14.3 When subjects withdraw, data collected prior to collection may be used for analysis, however they may exit the study at any point. Due to the compensation for the week 3, week 6, and long term follow up benchmarks, the subjects should be able to withdraw with no major issues.

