## **15.0 Risks to Subjects\***

15.1 There is a minimal risk for injury. Minimal risks that may occur related to study participation include muscle soreness during or after exercise, discomfort in joints of lower and upper extremity during or after exercise, which both are expected to occur infrequently.

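### Section 14.1 takes injured or no-longer-eligible participants out of the study, not only out of the exercises, and nothing in the plan keeps collecting their pain and disability scores

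*Combined protocol and SAP*

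**What the plan says.** The withdrawal rule in 14.1 reads: "If subjects no longer meet eligibility requirements or injure themselves, they will be withdrawn from the study by the principal investigator". Section 14.3 then deals with the data of people who leave: "data collected prior to collection may be used for analysis". The second *collection* there presumably means withdrawal. Nothing is said about scores after that point.

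Eligibility is described in 10.1 as a check made before enrolment: "Individuals will be screened for inclusion and exclusion criteria by self-reporting while reading the consent form and prior to giving consent". No later re-screening is scheduled. The exclusion criteria in section 10.0 include items that could change during the trial: "Current use of lidocaine patches or prescription pain medicine", "Currently seeing and or receiving care from an athletic trainer, physical therapist, or other rehabilitation specialist in the previous 6 months", "Unable to assume the exercise starting position" and "experiencing neurological symptoms or other muscular abnormalities".

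The primary objective in the Study Summary is change in pain and disability under the two programs. ODI and NPRS are scheduled in section 6.0 at baseline, 3 weeks and 6 weeks, and again through REDCap at 12, 18 and 24 months. Section 9.1 expects the primary analyses within 8 months of the start of enrolment. Section 17.1 names summary measures for the questionnaires but no analysis set and no missing-data method.

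**The concern.** Stopping an exercise program and leaving a trial are different events, and 14.1 treats them as one. A participant who is hurt while exercising, or whose back gets worse, may be exactly the person whose pain and disability scores matter most. If that person's follow-up ends because of what happened, the comparison is no longer between the groups as randomised.

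The loss need not be balanced. Both groups hold the exercises to discontinuation, but only the leaderboard group is shown others' hold times and encouraged to compete (5.1, 6.1). Injury could therefore differ by arm, although the documents give no rates. The sample-size allowance for attrition replaces numbers; it does not remove bias from outcome-related loss. Scores that were never collected cannot be recovered in the analysis.

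**Working it through.** **1. The plan's own figure.** Section 12.2 needs 34 evaluable participants and allows 15% attrition: 34 / (1 − 0.15) = 40, or 17 / 0.85 = 20 per group. This reproduces. The allowance covers 40 − 34 = 6 losses from all causes and is not tied to 14.1.

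**2. Is post-withdrawal collection provided anywhere?**
- 14.1 ends study participation.
- 14.3 covers only data already collected, and only permissively.
- 6.4 and 6.5 give a general questionnaire schedule and do not mention withdrawn people.
- 13.5 ties payment to completed milestones if someone withdraws. It does not say that withdrawn people are still assessed.
- 17.1 is silent.

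None of these restores ODI or NPRS after a 14.1 withdrawal.

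**3. Which triggers are firm?** Injury is named outright. The phrase about no longer meeting eligibility has meaning only after enrolment, but 10.1 applies the criteria before consent and no re-check is planned. The documents therefore do not settle whether starting pain medicine or rehabilitation care, for example, would trigger withdrawal.

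**4. Scores lost.** The first long-term questionnaire falls 12 months after a 6-week program, so it comes after the 8-month primary analysis. Three scores are due by then (baseline, week 3, week 6).

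| Withdrawn | Supplied for primary analysis | Long-term scores supplied |
|---|---|---|
| Before week 3 | 1 of 3 | 0 of 3 |
| Between weeks 3 and 6 | 2 of 3 | 0 of 3 |

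**5. Illustration of size; every input is assumed.** Take 20 per arm, normal outcomes with SD 1, no true effect, and 6 losses split 4:2. Removing w of 20 people whose mean lies k SD above the arm mean moves the mean of those remaining by −w × k / (20 − w).
- If those removed are exactly the worst scorers, the expected k for the top 4 of 20 standard normal values is 1.33, and for the top 2 it is 1.64.
- Arm losing 4: −4 × 1.33 / 16 = −0.33. Arm losing 2: −2 × 1.64 / 18 = −0.18.
- Difference: about 0.15 SD (0.153 by simulation).
- If removal correlates only 0.5 with outcome, k halves and so does the shift: about 0.08 SD (0.077 by simulation).
- Mirroring the split to 2:4 reverses the sign.

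For scale, the standard error with 16 and 18 remaining is √(1/16 + 1/18) = 0.34 SD. The shift is thus about 0.08 / 0.34 = 0.2 to 0.15 / 0.34 = 0.4 of a standard error.

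**6. When little happens.** Suppose one common rule acts in both arms and removes 2 of 40, with correlation 0.5. With no true effect there is no bias, and the error rate stays at 5%. A true 0.5 SD is estimated as 0.48. A true 0.99 SD is estimated as 0.95, with power 83% against 85% if the 2 losses were random. (0.99 SD is the effect implied by 17 per group and 80% power, if a two-sided two-sample t-test was used; 0.87 if one-sided. Section 12.0 names neither test nor sidedness.)

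**The case against.** The strongest reply is that the rule may hardly ever act. Section 15.1 describes minimal injury risk and names muscle soreness and joint discomfort, "which both are expected to occur infrequently". An injury need not involve the back, so a withdrawal need not relate to the outcome. The triggers most plausibly linked to outcome, such as pain medicine, rehabilitation care or neurological symptoms, all depend on reading the screening criteria as continuing requirements. Under a common rule that removes few people, the effect is negligible (step 6). If equal flares unrelated to treatment are removed from both arms, the estimate need not move at all: with assumed flares of 2 SD in 3 people per arm, 0.99 SD stays at 0.99 and power is 80%, against 73% with everyone kept.

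All of this stands, and it limits the size of the point. It does not close the gap: injury alone is an explicit, mandatory trigger, and no text keeps those participants under observation.

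Two stronger readings are tempting. A reader might infer that starting pain medicine or seeking care certainly ends participation; 10.1 and the absence of re-screening do not support that. A reader might also count the primary loss out of all six questionnaire times. Section 9.1 places the primary analyses before the 12-month round, so three is the better denominator. That section is not tidy, since it also expects the study to be completed within 8 months despite the 24-month follow-up.

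**Conclusion.** The point holds and should be fixed, with medium confidence. The textual gap is certain: followed as written, 14.1 ends primary-outcome collection after randomisation for a group that may be selected on outcome. Its practical size is unknown, because no section says how often the rule would act, in which arm, or on whom.

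The 0.08 to 0.15 SD shift rests entirely on the assumptions in step 5: all 6 allowed losses are 14.1 withdrawals, they split 4:2, and removal correlates with outcome between 0.5 and perfectly. A reader might infer something larger. If a common rule removed exactly the worst 6 of 40, a true 0.5 SD would be estimated as 0.33. That needs the whole attrition allowance to consist of 14.1 withdrawals, perfectly sorted by score, and nothing in the documents supports it. Nor do they support a claim that the trial will be biased toward either program.

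**What to change.** Leave decisions about continuing or stopping the exercises as they are, and change three passages.

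- **14.1:** reword the rule itself so that ending the exercise program is distinct from ending follow-up. State that participants stopped under 14.1 are still sent the ODI and NPRS through REDCap at 3 and 6 weeks and at 12, 18 and 24 months, unless they withdraw consent. A sentence added after an unchanged 14.1 would contradict it.
- **14.3:** state that data collected before withdrawal *will* be used, and correct the garbled wording.
- **17.1:** state that participants are analysed in their randomised group using all available scores. The choice of model is optional.

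Cost: for an assumed 2 to 6 such people, at most 2 × 5 = 10 to 6 × 5 = 30 extra questionnaire rounds, of which 2 × 2 = 4 to 6 × 2 = 12 fall at weeks 3 and 6. No extra visits are needed. The 13.5 payments attached to those rounds would apply, up to $75 per person (20 + 25 + 3 × 10), so $150 to $450 in all. A protocol amendment is needed, possibly with a consent change. Outcomes will also include the effect of any care started after randomisation, and the report should say so.
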